### 15.2 Best-Corrected Visual Acuity (ETDRS)

The visual acuity procedure will be performed at each visit pre-CAE®. The logarithm of the minimum angle of resolution (logMAR) VA must be assessed using an ETDRS chart. The procedure used will

be consistent with the recommendations provided for using the ETDRS eye chart. Visual Acuity should be evaluated at the beginning of each visit in the study (i.e., prior to slit-lamp examination). Subjects should use their most recent correction to attain their best-corrected visual acuity (BCVA).

The observed and change from baseline visual acuity will be summarized for each eye (study eye and fellow eye) using continuous descriptive statistics by visit for each treatment group. A subject listing of visual acuity will also be produced.

### **15.3 Slit-Lamp Biomicroscopy Examination**

A slit-lamp biomicroscopy examination of the cornea, conjunctiva, anterior chamber, iris, lens, and lid will be performed at each visit, and potentially at an Early Termination Visit. Both pre- and post-CAE® examinations will be made at Visits 1, 2, 4, 5, and 6. The results will be graded as normal, Abnormal Not Clinically Significant (NCS) or Abnormal Clinically Significant (CS). Abnormal findings will be described.

The results will be summarized using counts and percentages for each treatment group at each visit for each eye (study eye and fellow eye). Percentages will be based on the number of subjects in each treatment group with responses. Shift tables for the slit-lamp biomicroscopy parameters will also be provided comparing each follow-up visit to baseline. A subject listing of the slit-lamp biomicroscopy parameters will also be produced.

### **15.4 Dilated Fundoscopy Examination**

A dilated fundoscopy exam will be performed during the study post-CAE® at Visits 1 and 6, and potentially at an Early Termination Visit. Observations will be graded as Normal or Abnormal NCS or Abnormal CS. Abnormal findings will be described. The following will be examined:

- Vitreous
- Retina
- Macula
- Choroid
- Optic Nerve

The results will be summarized using counts and percentages for each treatment group at each visit for each eye (study eye and fellow eye). Percentages will be based on the number of subjects in each treatment group with responses. Shift tables for the undilated fundoscopy parameters will also be provided comparing Visit 6 to baseline (Visit 1). A subject listing of the undilated fundoscopy parameters will also be produced.

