4 OVERALL STUDY DESIGN

This is a Phase 2, multicenter, randomized, prospective, double-masked, placebo-controlled, parallel-arm design with block enrollment. Subjects will be randomized to one of the following treatment arms at Visit 2 and will be instructed to follow a BID-dosing regimen:

- HL036 0.25% Ophthalmic Solution (N~50)
- HL036 0.10% Ophthalmic Solution (N~50)
- Placebo, HL036 Ophthalmic Solution (N~50)

This study is multicenter, randomized, prospective, double-masked, placebo-controlled, parallel-arm design with block enrollment. Approximately 150 subjects will be randomly assigned to one of the three treatment groups (1:1:1) to receive either HL036 Ophthalmic Solution (0.10%, 0.25%) or placebo solution as topical ophthalmic drops administered bilaterally BID. Subjects, Sponsor, CRO and site personnel will be masked to treatment assignment.

[figure not shown]
During the screening period, two [REDACTED] exposures to the CAE® will be conducted to ascertain eligibility to enter the study. Those who qualify will be randomized to receive study drug in a double-masked fashion for 56 days. Subjects will self-administer drops twice daily and will complete daily diary assessments as instructed.

At Visits 4 (Day 15), 5 (Day 29) and 6 (Day 57), CAE® exposure will occur, with pre-CAE®, during CAE® (symptoms only) and post-CAE® assessments of ocular signs and symptoms. At Visit 3 only, no CAE® exposure will occur but signs and symptoms will be assessed.

The total number of expected participants, including screen failures, is approximately 375 subjects.

A study flow chart appears below:

Visit 1 (Day -14 ± 1): CAE® Screening	Informed Consent Demographics, Medical/Medication & Ocular History Urine Pregnancy Testing (as needed) Symptom Questionnaires, Visual Acuity Pre-CAE® Eye Evaluations CAE® Exposure Post-CAE® Eye Evaluations
------------------------------------------------------	----------------------------------------------------------------------------------------------------------------------------------------------------------------------------------------------------------------------------------------

Subjects who terminate early during the treatment period will be asked to complete safety assessments prior to commencement of any alternative dry eye therapy (if at all possible). Subjects who are terminated early from the study will not be replaced.

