### 15.5 Intraocular Pressure (IOP)

IOP will be measured in each eye by contact tonometry by the examiner and the results will be recorded in mmHg post-CAE® at Visits 1 and 6, and potentially at an Early Termination Visit. A single measurement is made to obtain a determination of IOP. The same tonometer employing the investigator's standard technique will be used throughout the study. In addition, all reasonable efforts will be made to have the same examiner obtain all IOP measurements for a given subject.

The IOP values and changes from baseline for each eye (study eye and fellow eye) will be summarized using continuous descriptive statistics by visit and eye for each treatment group and for all actively treated subjects. A subject listing of IOP will also be produced.

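### The fundus shift table is fixed to Visit 6, so a fundus exam at early termination cannot enter it, and the SAP gives no rule for early-termination IOP values

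*SAP*

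**What the plan says.** **When the exams are done.** SAP 15.4: "A dilated fundoscopy exam will be performed during the study post-CAE® at Visits 1 and 6, and potentially at an Early Termination Visit". SAP 15.5 gives IOP the same timing: "post-CAE® at Visits 1 and 6, and potentially at an Early Termination Visit". Protocol 4 supports this: "Subjects who terminate early during the treatment period will be asked to complete safety assessments", if at all possible. Protocol 5.5 likewise wants the termination-visit tests done when possible.

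**How fundoscopy is summarized.** Counts and percentages are given at each visit by arm and eye, with subjects who have responses as the denominator. The shift table is narrower: "Shift tables for the undilated fundoscopy parameters will also be provided comparing Visit 6 to baseline (Visit 1".

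**How IOP is summarized.** Values and changes from baseline are "summarized using continuous descriptive statistics by visit and eye for each treatment group and for all actively treated subjects".

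**General rules.** SAP 9.2 imputes no safety endpoint. SAP 4.1 labels visits in outputs by expected study day and tabulates Visits 1 to 6; it has no ET row and no rule for mapping ET or unscheduled records.

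**What the protocol promised.** Protocol 10.4.7 and the synopsis name visual acuity, slit lamp, dilated fundoscopy and IOP as safety endpoints, and then promise shifts from baseline to the worst on-treatment value for ocular safety assessments. No such output appears in SAP 15.4, SAP 15.5 or the SAP 19 table list. SAP 1 says its methods supersede the protocol's, and SAP 17 declares no changes.

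**The concern.** Fundoscopy and IOP each have one scheduled post-dose measurement, at Visit 6. For a subject who leaves before then, an ET exam is usually the only post-dose result. The plan expects such exams, yet the one table that shows change in fundus status is written so that it cannot use them. The slit-lamp shift table in SAP 15.3 compares every follow-up visit with baseline. The fundus table is tied to the final visit, although fundoscopy has no earlier scheduled post-dose exam.

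Leaving early need not be unrelated to safety. Protocol 5.5 lists a serious or intolerable AE among the withdrawal reasons, and Protocol 9.4 discontinues subjects who are unmasked for medical need. A table limited to those who reach Day 57 can therefore understate how often fundus status worsened. If the SAP 15.4 denominator rule also governs the shift table, early leavers drop out of numerator and denominator together, and the percentage does not show the gap.

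**Working it through.** **1. The plan's own figure.** SAP 6 gives 50 randomized per arm, 150 in total, and 10% dropout. 50 × (1 − 0.10) = 45 completers per arm, as the SAP states.

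**2. What each output does with an ET result.**

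| Output | Wording | ET result |
|---|---|---|
| Fundus shift table (SAP 15.4) | Visit 6 against Visit 1 | Cannot enter; no imputation |
| Fundus counts (SAP 15.4) | At each visit | No rule |
| IOP values and changes (SAP 15.5) | By visit and eye | No rule |
| Fundus and IOP listings (SAP 20) | By subject | Shown |
| Worst on-treatment shift (Protocol 10.4.7) | Not tied to a visit | Could enter, but not in the SAP |

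**3. Subjects affected.** Without a Visit 6 exam: 50 × 0.10 = 5 per arm and 150 × 0.10 = 15 overall. The shift table would hold about 45 of 50 per arm (135 of 150). If every early leaver had an ET exam, a last-exam table would hold up to 50 per arm (150), so 5 per arm is an upper bound. At an assumed dropout of 5% to 20%, the bound runs from 2.5 to 10 per arm and from 7.5 to 30 overall.

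**4. Effect on the reported rate (assumed rates; the documents give none).** Take an adverse fundus shift in 2% of completers and in a proportion p of early leavers, all of them examined at ET. The rate over all subjects is 0.9 × 2% + 0.1 × p. The share of shifts missed is 0.1 × p divided by that rate.

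| p | Rate, all subjects | Visit 6-only rate | Share missed |
|---|---|---|---|
| 2% | 2.0% | 2.0% | 10% |
| 10% | 2.8% | 2.0% | 36% |
| 20% | 3.8% | 2.0% | 53% |
| 40% | 5.8% | 2.0% | 69% |

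The first row shows that the rate is understated only if early leavers differ from completers.

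In single counts, one shift in an early leaver and none in completers gives 0/45 (0%) in the Visit 6 table, against 1/50 (2%) if all leavers are examined.

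**5. Precision.** With no events, the exact two-sided 95% upper limit is 1 − 0.025^(1/n): 7.9% for n = 45 and 7.1% for n = 50. The small difference shows that the issue is selective omission, not lost precision.

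**The case against.** The strongest reply is that little is lost, and most of it stands.

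- A reader might infer that ET values for IOP and the fundus counts are dropped too. The documents do not say so. SAP 15.5 names the ET Visit as a measurement occasion and then summarizes by visit, which could include an ET row. The SAP 4.1 table labels scheduled visits; it does not say which records are analysed. What is missing there is a rule.
- The data are not lost. Both measures are listed by subject (Listings 16.2.8.3 and 16.2.8.4). Protocol 9 requires any clinically relevant deterioration to be recorded as an AE, so a clinically significant fundus change in an early leaver should also appear in the ocular TEAE tables.
- The ET exam is not always the only post-dose exam. Protocol 8.4.2 lets unscheduled visits include both tests.
- A reader might infer that the comparison between arms is biased toward safety. No between-arm test is planned for either measure, and a distorted arm difference would need the omitted shifts to differ between arms, for which the documents give no basis.
- Five per arm is not an expected count. ET exams are done only potentially or when possible, and discontinuation includes loss to follow-up.
- A reader might take the protocol's worst-value shift to concern only repeatedly measured endpoints such as slit lamp and visual acuity. Protocol 10.4.7 names fundoscopy and IOP alongside them and sets no such limit. Restoring that shift would resolve most of the problem.

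None of this lets an ET fundus exam into the shift table as it is now defined.

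**Conclusion.** The point holds for the fundus shift table, where exclusion follows from the stated comparison and the no-imputation rule. For IOP and the by-visit fundus counts, it holds only as a missing rule for ET and unscheduled values. The SAP also omits the protocol's worst on-treatment shift, which could have captured these values, without declaring the change.

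The size is at most about 5 of 50 per arm (15 of 150). This rests on the planned 10% dropout and on every early leaver having an ET exam. The consequence is possible understatement in a descriptive safety table, and only if early leavers have more fundus shifts than completers. The documents do not support reading it as lost safety data or as a demonstrated bias between arms. It is still worth correcting before unmasking, because the correction needs no new data.

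**What to change.** 1. In SAP 15.4 and 15.5, define the last post-dose exam: Visit 6, otherwise the ET or an unscheduled exam. Base the fundus shift table and an IOP change-from-baseline row on it, and show the Visit 6-only result alongside. Alternatively, restore the protocol's worst on-treatment shift for both measures, with on-treatment defined so that it is clear whether ET exams count.
2. State how ET and unscheduled values enter the by-visit fundus and IOP tables.
3. If the worst on-treatment shift is not restored, declare its removal in SAP 17.
4. In SAP 15.4, change *undilated* to *dilated* in the shift-table and listing sentences; the section and its exam are dilated.

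The cost is SAP wording and one derived record per subject, with no new data. The downside is that an end-of-treatment value mixes exposure lengths, which the Visit 6-only result makes visible.

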### 15.5 Intraocular Pressure (IOP)

IOP will be measured in each eye by contact tonometry by the examiner and the results will be recorded in mmHg post-CAE® at Visits 1 and 6, and potentially at an Early Termination Visit. A single measurement is made to obtain a determination of IOP. The same tonometer employing the investigator's standard technique will be used throughout the study. In addition, all reasonable efforts will be made to have the same examiner obtain all IOP measurements for a given subject.

The IOP values and changes from baseline for each eye (study eye and fellow eye) will be summarized using continuous descriptive statistics by visit and eye for each treatment group and for all actively treated subjects. A subject listing of IOP will also be produced.

### 15.6 Immunogenicity to HL036 in Serum

Analyses of immunogenicity data will be conducted as ad-hoc analyses. The anticipated ad-hoc analyses of immunogenicity are as follows.

Immunogenicity will be summarized using discrete summary statistics. Counts and proportions of patients with anti-drug antibodies (ADA) will be presented by visit and treatment group. Exact 95% Clopper-Pearson confidence intervals will be presented. Treatment groups will be compared using Fisher's Exact Test, and exact 95% confidence intervals for the pairwise proportion differences will be constructed.

Antibody titer of patients positive for ADA will be summarized using continuous descriptive statistics and presented by visit and treatment group. Treatment groups will be compared using two-sample t-tests. The differences in means, two-sided 95% confidence intervals (CIs) for the difference in means and p-values will be reported. Wilcoxon rank sum tests will also be conducted.

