6.2 SAFETY MEASURES

- Incidence and severity of ocular AEs
- Incidence and severity of non-ocular AEs
- BCVA at all visits
- Slit-lamp biomicroscopy at all visits
- Drop comfort assessment (Visits 2)
- Intraocular pressure (Visits 1 and 6)
- Dilated fundoscopy (Visits 1 and 6)
- Immunogenicity to HL036 in Serum (Visits 2, 4, 5, and 6)

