7.1.3 Instructions for Use and Administration

- Study drug will be supplied as a sterile, clear, colorless liquid solution containing 0.25% or 0.10% API (HL036) 5 cavity, 0.5 mL low-density polyethylene (LDPE) unit dose vials with a fill volume of approximately 0.25 mL. Each mL of the 0.25% solution contains 2.5 mg of the API, and each mL of the 0.10% solution contains 1.0 mg of the API. In addition to HL036, the components of the drug product solution are: sodium chloride (tonicity adjusting agent), citric acid

monohydrate (buffering solution), sodium hydroxide solution and hydrochloric acid 1% (both for pH adjustments), and sterile water for injection as a solvent.

- The placebo solution consists of all components of the drug product solution with the exception of HL036.
- At the study site, all IP must be stored under the conditions specified in the Investigator's Brochure in a secure area accessible only to the designated qualified clinical site personnel. All IP must be stored, inventoried and the inventories carefully and accurately documented according to applicable state, federal and local regulations, ICH GCPs and study procedures.
- HL036 and placebo solutions should be stored refrigerated (2–8° C). Subjects will be instructed to store HL036 and placebo solutions in a refrigerator (2–8° C). It is recommended that HL036 and placebo solutions be placed at room (ambient) temperature at least 1 ± 0.5 hours prior to administration to subjects. Sterile drug product and placebo solutions are packaged into single-use 0.5 mL LDPE unit dose vials that deliver an approximate per drop volume of 50 µL. Two cavity unit dose vials are packaged in aluminum foil pouches under nitrogen. Unit dose vials are for SINGLE USE ONLY.
- At a minimum, the immediate or secondary study drug packaging will provide the following information: study sponsor identification, batch number, directions for use, required storage conditions, caution statements (including "New Drug—Limited by Federal Law to Investigational Use" language), study identification and product retest date.

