8.3 EXAMINATION PROCEDURES

An ICF must be signed and dated by the subject, the PI or designee and witness (if required) before any study-related procedures are performed.

Procedures listed below should be performed in the given order. See **Appendix 2** for details on methodologies and grading systems.

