8.3.2 Visit 2: Day 1 – CAE® Confirmation and Baseline

Pre-CAE®

- Study Diary/Placebo Collection Subject study diaries and all used/unused placebo vials dispensed for Days –14 to 1 should be collected and reviewed by a trained study technician.
- Site staff must confirm subjects have NOT administered their morning placebo dose at home.
- Review of Inclusion/Exclusion Criteria
- Monitoring and Query of AEs Report any AEs that occur after signing the ICF.
- Record all Changes in Concomitant Medications
- Ora Calibra® Ocular Discomfort Scale
- Ora Calibra® Ocular Discomfort and 4-Symptom Questionnaire Ocular Discomfort Score
- VAS discomfort scale
- OSDI
- BCVA Utilizing an ETDRS Chart
- Slit Lamp Biomicroscopy
- Conjunctival redness
- Tear sample collection from both eyes
- TFBUT
- Fluorescein Staining
- Lissamine Green Staining

Confirmatory Screening Challenge (CAE® #2)

Subjects will be exposed to the CAE® for [REDACTED]. Ocular discomfort self-assessment scores (ODS) will be obtained just prior to entering, during and just after the CAE® exposure. During the CAE® exposure, ODS will be collected at [REDACTED]
[REDACTED].

Post-CAE®

- Inclusion/Exclusion Evaluation
- Ora Calibra® Ocular Discomfort Scale
- Ora Calibra® Ocular Discomfort and 4-Symptom Questionnaire Ocular Discomfort Score
- VAS discomfort scale

- Slit Lamp Biomicroscopy
- Conjunctival redness
- TFBUT
- Fluorescein Staining
- Lissamine Green Staining
- Schirmer's test
- Review of Inclusion/Exclusion Criteria
 - Eligible subjects must replicate a positive response at this visit in the same eye as was elicited in Visit 1. A positive response is defined as meeting ALL of the following criteria in the same eye:
 - Having at least a [redacted] point increase in fluorescein staining in the inferior region in at least one eye following CAE® exposure;
 - Reporting an Ocular Discomfort score [redacted] at 2 or more consecutive time points in at least one eye during CAE® exposure [redacted]
[redacted]
[redacted]

Randomization

- Blood sampling for Immunogenicity testing
- Study Drug Instillation at the Study Site All subjects having a positive response (as defined above) and meeting all other screening eligibility criteria after Visit 2 will be randomized to one of three treatment arms. Randomized subjects will self-administer their initial study drug dose bilaterally at the study site.

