10.4.7 Safety Variables

Adverse events will be coded using the MedDRA dictionary. Frequencies and percentages of subjects with treatment-emergent adverse events (TEAEs), serious TEAEs, and TEAEs causing premature discontinuation will be provided by treatment group. An AE is treatment emergent if it 1) occurs after the first dose of randomized study treatment or 2) if it is present prior to receipt of randomized study treatment but worsens in severity or increases in frequency after the first dose of randomized study treatment. Furthermore, frequencies will be given of subjects with TEAEs by system organ class and preferred term; by system organ class, preferred term and maximal severity; by system organ class, preferred term for treatment-related AEs; by system organ class and preferred term for SAEs; and by system organ class, preferred term, and day of onset. Separate analyses will be performed for ocular specific and all AEs (including systemic).

Other safety endpoints including visual acuity, slit lamp biomicroscopy, dilated fundoscopy, and intraocular pressure, will be summarized by treatment group and visit using descriptive statistics. Changes or shifts from baseline will also be summarized where appropriate. For assessments performed by eye, study eye and fellow eye will be summarized separately. In addition, shifts from baseline to worst on-treatment value for ocular safety assessments will be summarized.

Immunogenicity will be summarized using discrete summary statistics. Counts and proportions will be presented by visit and treatment group. Exact 95% Clopper-Pearson confidence intervals will be presented. Treatment groups will be compared using Fisher's Exact Test, and exact 95% confidence intervals for the pairwise proportion differences will be constructed.

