Observations will be graded as Normal or Abnormal. Abnormal findings that are clinically significant (as determined by the investigator that may interfere with study parameters or otherwise confound the data) and those that are not clinically significant will be described. A dilated fundoscopy examination should be performed if retinal disease is detected.

- Vitreous: Examination should emphasize the visual axis.
- Retina, Macula, Choroid: Include an observation of the retina and its blood vessels. Eyes should be excluded from the study if active inflammation is present.
- Optic Nerve: Significant damage or cupping to the optic nerve should be noted.

It is recommended that tropicamide 1% ophthalmic solution be used to dilate subjects. The use of cyclopentolate 1% ophthalmic solution is recommended as secondary dilating medication, should the need arise.

Intraocular Pressure

Intraocular pressure (IOP) will be measured in each eye by contact tonometry by the examiner and the results will be recorded in mmHg. A single measurement is made to obtain a determination of IOP. The same tonometer employing the Investigator's standard technique will be used throughout the study. In addition, all reasonable efforts will be made to have the same examiner obtain all IOP measurements for a given subject.

Tear Collection

Subjects will be seated at a reclined position. The investigator will collect tears for up to 5 min from each eye. The right eye will be collected, followed by the left eye. Once tears are collected, they will be pipetted into a separate tube for storage. Further details on tear collection process and storage will be found in a separate manual.

Blood Sampling for Immunogenicity Testing

Serum blood draws will be collected at Visits 2, 4, 5 and 6 for immunogenicity testing. Instructions for the collection, handling and shipping blood for immunogenicity testing are given in a separate laboratory manual.

Ora proprietary scales – Not for distribution without permission

Ora Calibra® Ocular Discomfort Scale for Dry Eye

Ora Calibra® Ocular Discomfort & 4-Symptom Questionnaire for Dry Eye

Visual Analogue Scale (VAS)

Subjects will be asked the following questions regarding ocular discomfort (unrelated to study drug instillation) at all visits.

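### Anti-drug antibodies are compared only as prevalence by visit and arm, with no link to each subject's own pre-dose result and no count of subjects ever positive after dosing

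*SAP*

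**What the plan says.** Immunogenicity is a named safety measure in Protocol 6.2: "Immunogenicity to HL036 in Serum (Visits 2, 4, 5, and 6"). Protocol Appendix 2 confirms the sampling: "Serum blood draws will be collected at Visits 2, 4, 5 and 6 for immunogenicity testing".

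The analysis rule in Protocol 10.4.7 is "Counts and proportions will be presented by visit and treatment group", with Clopper-Pearson intervals, Fisher's exact test between arms and exact intervals for pairwise differences. SAP 15.6 repeats it: "Counts and proportions of patients with anti-drug antibodies (ADA) will be presented by visit and treatment group". It adds a titre summary, also by visit, restricted to ADA-positive subjects. It gives the whole set a provisional status: "Analyses of immunogenicity data will be conducted as ad-hoc analyses". The SAP table list (section 19) contains no ADA table, and the only immunogenicity item in the listings (section 20) is a record of blood draws.

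The Visit 2 sample is a true HL036-naive baseline:
- Protocol 8.3.2 lists "Blood sampling for Immunogenicity testing" ahead of the first instillation of randomized drug.
- Protocol 8.3 makes the sequence binding: "Procedures listed below should be performed in the given order".
- The run-in drops are placebo, and Protocol 7.1.3 says "The placebo solution consists of all components of the drug product solution with the exception of HL036".

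Neither document defines treatment-induced or boosted ADA, compares a later result with the subject's own Visit 2 result, or counts subjects positive at any post-dose visit.

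**The concern.** For an engineered protein, the safety question is whether dosing induces antibodies, and in how many subjects. Prevalence at a visit answers a different question. It mixes reactivity present before dosing with reactivity caused by dosing, and it treats each visit as a separate snapshot.

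Other safety data in the same SAP are referred to baseline. Adverse events have a treatment-emergent definition (15.1), slit lamp and fundoscopy have shift tables (15.3, 15.4), and visual acuity and IOP have change from baseline (15.2, 15.5). ADA is the exception, although the pre-dose sample is taken.

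Two things are at stake. Background positives in every arm make an induced difference harder to see. And a run of low by-visit percentages can conceal a larger share of subjects who were positive at some point.

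**Working it through.** **The plan's own figure.** Neither document states an ADA rate, power or sample size, so there is nothing to reproduce.

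**Inputs from the documents.** 50 randomized per arm and 45 expected completers (Protocol 10.3, SAP 6); two-sided tests at 0.05 (SAP 9.4); Fisher's exact test (SAP 15.6); three post-dose samples, at Visits 4, 5 and 6.

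**Assumed inputs.** Baseline prevalence b from 0% to 15%, equal across arms by randomization; induction in 15% of baseline-negative HL036 subjects; no induction on placebo; baseline positives stay positive and are not boosted.

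**1. Effect of pre-existing positives**

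All positives at a post-dose visit:
- HL036 = b + (1 − b) × 0.15
- placebo = b

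Treatment-emergent positives, with all 50 in the denominator:
- HL036 = (1 − b) × 0.15
- placebo = 0

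Example at b = 10%: all positives are 0.10 + 0.90 × 0.15 = 23.5% against 10%; treatment-emergent positives are 0.90 × 0.15 = 13.5% against 0%.

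The expected difference is 13.5 points either way, below the 15 points that apply to baseline-negative subjects. The two definitions differ in the background: 13.5 points over 10% is harder to detect than 13.5 points over zero.

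Exact Fisher power at 50 per arm, by full enumeration of both binomials:

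| Baseline prevalence | HL036 v placebo, all positives | Power, all positives | HL036 v placebo, treatment-emergent | Power, treatment-emergent |
|---|---|---|---|---|
| 0% | 15.0% v 0% | 0.78 | 15.0% v 0% | 0.78 |
| 1% | 15.9% v 1% | 0.69 | 14.9% v 0% | 0.77 |
| 5% | 19.3% v 5% | 0.47 | 14.3% v 0% | 0.74 |
| 10% | 23.5% v 10% | 0.34 | 13.5% v 0% | 0.68 |
| 15% | 27.8% v 15% | 0.27 | 12.8% v 0% | 0.63 |

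At 45 per arm and 5% prevalence the powers are 0.44 and 0.63.

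In counts: 6/50 new positives on HL036 against 0/50 on placebo gives p = 0.027. Add two pre-existing positives to each arm and the comparison becomes 8/50 against 2/50, with p = 0.092. The same six conversions no longer stand out.

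**2. Effect of not combining visits**

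Suppose 3/50 HL036 subjects are positive at each of Visits 4, 5 and 6, all were negative at Visit 2, and placebo has 0/50. Every visit then shows 6% (exact 95% interval 1.3% to 16.5%; p = 0.24 against 0/50).

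- Same three subjects throughout: ever positive = 3/50 = 6%. Nothing is understated.
- Different subjects each time: ever positive = 3 + 3 + 3 = 9/50 = 18% (exact 95% interval 8.6% to 31.4%; p = 0.003 against 0/50).
- Statistically independent visits, as a middle case: 1 − (1 − 0.06)³ = 16.9%.

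The planned by-visit summaries look identical in the first two cases.

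**The case against.** A reader might infer that pre-existing antibodies count against HL036. The documents do not support that. Allocation is 1:1:1, so such positives fall on placebo as well. They raise the HL036 percentage read alone but on average blur the comparison, which favours HL036. Only a chance imbalance would work against it.

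A reader might also infer that the Visit 2 sample goes unused. It does not: Visit 2 is one of the planned sampling visits, so its prevalence by arm, including any imbalance, is part of the by-visit output. What is missing is the link within subject. Marginal proportions at two visits cannot show who converted.

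The stronger objections concern size and consequence. The rates are assumed; with no pre-existing reactivity there is no loss, and at 1% it is modest. The threefold gap between by-visit and cumulative figures needs wholly transient positivity in different subjects. ADA is outside the success criterion, has no power target, and sits in a trial that SAP 9.5 describes as mainly exploratory. SAP section 1 permits supplementary analyses, so a treatment-emergent count could be added later.

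All of that stands and limits the weight of the point. It does not remove it: a definition added after unmasking, including the titre rise that counts as boosting, could be chosen with the results in view.

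**Conclusion.** The point holds as a cheap improvement to a safety analysis; the primary efficacy analyses are unaffected. The planned ADA summary cannot separate induced from pre-existing antibodies at subject level and gives no per-subject incidence after dosing.

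The direction of the first problem is towards hiding an HL036 effect. Its size depends on a baseline prevalence that the documents do not give. Under the stated assumptions the power lost by counting all positives is nil at 0% prevalence, about 0.08 at 1% (0.77 − 0.69), 0.27 at 5% (0.74 − 0.47) and 0.34 at 10% (0.68 − 0.34).

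The second problem is conditional. Per-subject risk is understated if positivity is transient, or if positive subjects drop out before later samples. It is not understated if positivity persists to Visit 6 and subjects remain under observation.

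**What to change.** Before unmasking, amend SAP 15.6 as follows:

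- Define treatment-emergent ADA against Visit 2: negative at Visit 2 and positive at any post-dose visit or, if positive at Visit 2, a titre rise of a size fixed in advance.
- Report its incidence per arm, counting each subject once, among subjects with a Visit 2 sample and at least one post-dose sample. Use the Clopper-Pearson intervals and Fisher test already planned.
- Keep prevalence by visit, including Visit 2, as supportive.
- Add the table to SAP section 19 and make it a planned safety output instead of an ad hoc one.

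The cost is SAP wording and one table. All the samples needed are already in the visit schedule.
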